#### **Table 1-4 CMD date imputation**

# 3.8 Visit windows and cutoffs for efficacy and safety analyses

This section defines the data cutoffs within which data will be included in the analysis and time points for which data will be summarized.

Due to the study design, both data collected at Month 12 visit as end of the treatment (EOT) (also as end of study (EOS) visit) and data collected at the study drug discontinuation visit as EOT will be recorded in the CRF at EOT (corresponding to Visit 777 in the database). For subjects who discontinue study drug early but continue through the study per abbreviated schedule, the EOT visit and EOS visit may be different, in which case data collected at the EOS visit will be recorded in the CRF at study completion visit (corresponding to Visit 778 in the database). For subjects whose EOT visit and EOS visit are the same, data will be collected only once at the EOT visit. Therefore, there will be no corresponding Visit 778 in the database for these subjects. In the subject completion (CMP) data set, data collected from the study drug discontinuation CRF (Visit 777) and study completion CRF (Visit 778) will be differentiated by visit number although there is no actual study visit corresponding to Visit 778 for subjects whose EOT visit and EOS visit are the same.

#### 3.8.1 Study Day 1 and other study days

The first day of administration of randomized study medication (i.e., the first dose date of the study drug) is defined as Study Day 1 or Day 1.

All other study days will be labeled relative to Day 1. For event dates on or after Day 1, study day for an event date is calculated as (event date – first dose date +1), which could be Day 1, Day 2, Day 3, etc. For event dates before Day 1, study day for an event date is calculated as (event date – first dose date), which could be Day -1, Day -2, etc., referring to one day, two days, etc., before Day 1, respectively. Duration of an event will be calculated as (event end date – event start date + 1).

One month is defined as 30 days.

#### 3.8.2 Screening/Baseline

Screening refers to any procedures (e.g. checking inclusion and exclusion criteria) performed prior to first dose date. Subject informed consent is generally obtained prior to any assessment. Any assessment obtained prior to first dose date will be called screening assessment.

In general, a baseline value refers to the last measurement made prior to the administration of the first dose of the study drug. Assessments made on Day 1 may occur before or after the first dose. The following rules will be applied to determine which record is the last measurement prior to the first dose (i.e., the baseline value).

- Consider all records with an assessment date before or on the first dose date. Baseline is the
  last record after sorting all above records with respect to assessment date, visit and repeat
  visit number.
- Some data specific rules for determining baseline will be applied as described below or in data specific sections if applicable.

For vital signs, the average of the 3 readings from Day 1 pre-dose at each position (sitting, supine or standing) will be used as baseline for that position. If unavailable, the last available average value from visits (including unscheduled) before the first dose will be used. For sitting pulse the last available single value before the first dose will be used as baseline.

For ECG, the Day 1 pre-dose value will be used as baseline. If unavailable, the last available (including unscheduled) value before the first dose will be used.

The pre-dose time point is the record at scheduled time point 0 (i.e., variable STM2N equals 0).

#### 3.8.3 Nominal visits and visit windows

#### 3.8.3.1 Nominal visits

For EDSS, PRO variables (except C-SSRS), dermatology exam, MRI and OCT, the nominal visit will be used in the by-visit summaries. Data from unscheduled visits for these assessments will not be summarized unless otherwise specified.

The end of treatment or early discontinuation visit (Visit 777) will be the nominal 12 month visit for subjects who complete the study on study drug. For subjects who discontinue the study drug prematurely, the end of treatment or early discontinuation visit (Visit 777), the follow-up visit (Visit 501) and the end of study visit (Visit 778) which are not timepoint specific visits will be remapped based on the following rules:

• If these visits fall into a specific visit window and the corresponding scheduled visit is missing, then these visits will be remapped to be that scheduled visit. The visit windows are defined as within 5 days of the scheduled visit (+/-5 days from the target day at each visit).

- If these visits fall into a specific visit window and the corresponding scheduled visit (e.g., Visit X) is not missing, then these visits will be assigned a visit number with a decimal place where the visit number depends on whether the corresponding scheduled visit occurs before (e.g., Visit X.1 or Visit X.2 if Visit X.1 already exist etc.) or after these visits (e.g., Visit X-1.1 or Visit X-1.2 if Visit X-1.1 already exist etc.)
- If these visits do not fall into a specific visit window but fall in between 2 consecutive scheduled visit windows (e.g., between visit windows of Visit X and Visit X+1), then these visits will be assigned a visit number with a decimal place (e.g., Visit X.1 or Visit X.2 if Visit X.1 already exist etc.).

The remapped visits (e.g., Visit X) will be treated as nominal visits in the by-visit summaries.

For dermatology exam and OCT the above visits (Visit 777, Visit 501 and Visit 778) will not be remapped.

#### **Table 2-2 Visit windows for PFTs**

Visit	Start day	Target Day	End day
Month 6	1	180	270
Month 12	271	360	last dose date day +45
Last dose date day +			
Follow-up	46	450	

# Table 2-3 Visit windows for ophthalmologic examination (excluding OCT)

Visit	Start day	Target Day	End day
Month 3	1	90	135
Month 6	136	180	270
Month 12	271	360	last dose date day +45
	Last dose date day +		
Follow-up	46	450	

#### **Table 2-4 Visit windows for ECG**

Visit	Start day	Target Day	End day
Month 12	1	360	last dose date day +45
Last dose date day +			
Follow-up	46	450	

#### **Table 2-5 Visit windows for C-SSRS**

Visit	Start day	Target Day	End day
Screening	-45	NA	-1
Baseline	1	1	1
Month 1	2	30	60
Month 3	61	90	135
Month 6	136	180	225
Month 9	226	270	315
Month 12	316	360	last dose date day +45
	Last dose date day +		
Follow-up	46	450	

#### 3.8.4 Time points for first dose monitoring ECG and Vital signs

For the first dose monitoring ECG, data will be summarized for the following time points:

- Day 1 pre-dose: day 1 ECG value at 0 hour per time label
- Day 1 post-dose (6 hours): day 1 ECG value at 6 hours per time label.
- Day 1 post-dose (>6 hours): the mean of all day 1 ECG values after 6 hours per time label (including unscheduled values).

Unscheduled ECG measured between the day 1 pre-dose and the 6 hours post-dose will not be summarized but reported in the data listing only. For the second dose monitoring ECG, data will be summarized similarly.

For the first dose monitoring vital signs, data will be summarized for the following time points:

- Day 1 pre-dose: day 1 vital sign value at 0 hour per time label
- 1 hour post-dose
- 2 hours post-dose
- 3 hours post-dose
- 4 hours post-dose
- 5 hours post-dose
- 6 hours post-dose

The vital sign values at specified hours per time label post-dose will be used. Extended first dose monitoring after the 6 hours post-dose will not be summarized but reported in the data listing only. For the second dose or restart dose monitoring vital signs, data will be summarized similarly.

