5.5.5 Guidelines for monitoring patients taking their first dose of fingolimod

The patient will stay at the site for a minimum of 6 hours after the first dose of fingolimod to be monitored for signs and symptoms of bradycardia. All fingolimod patients will have an ECG performed prior to dosing and at the end of the 6-hour monitoring period. (Glatiramer acetate patients will have a single ECG during the randomization visit.) The treating physician is responsible for monitoring the patient following the first intake of fingolimod, as well as managing bradycardia symptoms should they occur. He or she must review vital signs during the 6-hour monitoring, post-dose ECG and assess discharge criteria at 6 hours after dosing.

Baseline or predose ECG should be provided by the site and be available for comparison to the postdose ECG in order to determine if discharge criteria are met.

Heart rate and blood pressure should be measured before the first dose of fingolimod, then every hour for at least 6 hours thereafter (by the treating physician or an assisting nurse). Blood pressure will be measured in the supine position and then the standing position at each time point. When obtaining the predose heart rate before the first dose, the patient should be allowed to rest in the supine position for 5 minutes before taking the heart rate. The heart rate and blood pressure measurements should be repeated twice to produce 3 baseline readings in the supine position for both heart rate and blood pressure (before the first dose of fingolimod only). Heart rate and blood pressure will then be measured in the same manner (i.e., 3 baseline readings) with the patient in the standing position before the first dose of fingolimod. For comparison to the postdose heart rate values, the lowest predose supine value and lowest predose standing value of heart rate should be used. Patients should receive the first dose of fingolimod before 12:00 PM (noon) in the outpatient setting.

Patients may be discharged after 6 hours ONLY if ALL of the following criteria are met:

- supine heart rate must be at least 45 beats per minute
- heart rate must not be the lowest hourly value measured during the observation period (which would suggest that nadir may not have been reached)
- patients must have no symptoms associated with decreased heart rate or must not have received treatment for bradycardia

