- ECG at 6 hours after dosing should not show any new significant abnormalities (e.g., onset second-degree or third-degree AV block, QTc ≥500 msec) other than sinus bradycardia, that were not also observed at the patient's predose ECG

If the discharge criteria listed above are not met after 6 hours, observation must be continued until symptoms resolve.

If a patient requires treatment for bradycardia/bradyarrhythmia during the first dose observation, the patient should be monitored overnight, and the 6-hour monitoring procedure should be repeated for the second dose of study drug.

If a patient experiences a QTc interval greater than or equal to 500 msec at 6 hours after the first dose, the patient should be monitored overnight, and the 6-hour monitoring procedure should be repeated for the second dose of study drug.

Patients with some pre-existing conditions (e.g., ischemic heart disease, history of myocardial infarction, congestive heart failure, history of cardiac arrest, cerebrovascular disease, uncontrolled hypertension, history of symptomatic bradycardia, history of recurrent syncope, severe untreated sleep apnea, AV block, sinoatrial heart block) may poorly tolerate the fingolimod-induced bradycardia, or experience serious rhythm disturbances after the first dose of fingolimod. Prior to treatment with fingolimod, these patients should have a cardiac evaluation by a physician appropriately trained to conduct such evaluation, and, if treated with fingolimod, should be monitored overnight with continuous ECG in a medical facility after the first dose.

Since initiation of fingolimod treatment results in decreased heart rate and may prolong the QT interval, patients with a prolonged QTc interval (>450 msec males, >470 msec females)

before dosing or during a 6-hour observation period, or at additional risk for QT prolongation (e.g., hypokalemia, hypomagnesemia, congenital long-QT syndrome), or on concurrent therapy with QT-prolonging drugs with a known risk of torsades de pointes (e.g., citalopram, chlorpromazine, haloperidol, methadone, erythromycin) should be monitored overnight with continuous ECG in a medical facility.

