## 8.4 Electrocardiograms (ECG)

The ECG data includes quantitative variables such as ventricular rate, PQ or PR interval, R-R interval, QRS duration, and uncorrected QT interval as well as categorical variables such as ECG interpretation (normal or abnormal), ECG evaluation type (rhythm, conduction, etc) and ECG findings (prolonged QTc, low voltage, etc).

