## 8.8.4 Data summaries for first dose monitoring

Summaries on the safety set by treatment group include:

- Summary statistics of vital signs by hour (1st dose, 2nd dose, and restarts)
- Changes from pre-dose in vital signs by hour (1st dose, 2nd dose, and restarts)
- Frequency (%) distribution of categorized supine and standing pulse or change (or percent change) from pre-dose supine and standing pulse during first dose administration, respectively
- Summary of the overall dose monitoring experience (1st dose, 2nd dose, and restarts)
- Incidence rates of bradycardia events (1st dose and 2nd dose)
- Incidence rates of medications used for bradycardia (1st dose and 2nd dose)

- Incidence rates of bradycardia symptoms by SOC, PT, and severity (1st and 2nd dose)
- Incidence rates of notable vital sign abnormalities based on the notable criteria in Table 4-5 (1st dose and 2nd dose)
- Summary statistics of ECG parameters by time point during 1st and 2nd dose administration
- Changes from pre-dose in ECG parameters by time point during 1st and 2nd dose administration
- Incidence rates of abnormal QTc interval (Bazett and Fridericia) as defined by the abnormality criteria in Table 4-6 during 1st and 2nd dose administration
- Frequency (%) distribution of ECGs interpretation (normal/abnormal) by time point during 1st and 2nd dose administration
- Frequency (%) distribution of ECG findings by ECG evaluation type by time point during 1st and 2nd dose administration

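### First-dose pulse and blood-pressure summaries stop at 6 hours and omit unscheduled ECGs before then, so the tabulated maximum fall and QTc incidence can only equal or understate what was measured

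*SAP*

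**What the plan says.** **Vital signs.** SAP 3.8.4 sets the first-dose time points as pre-dose and each hour from 1 to 6. Of later readings it says: "Extended first dose monitoring after the 6 hours post-dose will not be summarized but reported in the data listing only". Second-dose and restart-dose vital signs are to be summarised in the same way.

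**ECG.** The same section has rows for pre-dose, 6 hours and later than 6 hours. The last row is "the mean of all day 1 ECG values after 6 hours per time label (including unscheduled values"). For the interval before 6 hours: "Unscheduled ECG measured between the day 1 pre-dose and the 6 hours post-dose will not be summarized but reported in the data listing only".

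**Who is observed for longer.** One of the protocol 5.5.5 conditions for discharge at 6 hours is that "heart rate must not be the lowest hourly value measured during the observation period (which would suggest that nadir may not have been reached"). The others are a supine rate of at least 45 bpm, no symptoms of or treatment for a low rate, and no new significant ECG abnormality. Then: "If the discharge criteria listed above are not met after 6 hours, observation must be continued until symptoms resolve".

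**What is built from these data.** SAP 8.8.4 plans hourly summaries, categorised pulse and change from pre-dose, "Incidence rates of notable vital sign abnormalities based on the notable criteria in Table 4-5" and the incidence of abnormal QTc, all as descriptive safety output.

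**The concern.** The protocol treats a 6-hour heart rate that is the lowest so far as a sign that the trough may still lie ahead, and holds the patient for that reason. The SAP then leaves the readings taken during that extra observation out of every vital-sign table. Whether a pulse or blood-pressure reading is summarised therefore depends in part on how the patient's heart rate behaved, so the omission is informative.

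At stake is the description of first-dose effect: how low pulse and blood pressure went, how large the maximum change was, and how many patients crossed a Table 4-5 limit. A similar question arises for QTc, where a count of patients above a threshold should rest on the highest value recorded.

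**Working it through.** The plan gives no figure on this point, so the check sets the passages side by side and follows their logic.

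**1. Does another table recover the later readings?** No vital-sign table does. SAP 8.3.3 excludes hourly dose-monitoring data from the routine vital-sign summaries. SAP 3.8.6 exempts first-dose, second-dose and restart-dose data from its rules for multiple assessments. The ECG data do include heart rate ("The ECG data includes quantitative variables such as ventricular rate", SAP 8.4), so some rate information after 6 hours is summarised. But it is one mean per patient, which does not show a trough. Protocol 5.5.5 schedules the ECG before dosing and at 6 hours, and sets no later ECG for a patient kept only because the 6-hour rate was the lowest.

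**2. Direction of the effect.** Let P be the pre-dose value, L6 the lowest reading in hours 1 to 6, and L+ the lowest reading after 6 hours.

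- Tabulated fall = P − L6
- Measured fall = P − min(L6, L+)
- Measured minus tabulated = max(0, L6 − L+), which is never negative

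For a patient held because the 6-hour rate was the lowest, L6 is the 6-hour reading itself, and any lower value can only be among the readings left out.

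**3. Effect on the Table 4-5 pulse criterion** (below 50 bpm, or a fall of 15 bpm or more).

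- A patient held because supine rate was below 45 bpm is already below 50 and is already counted. Only the depth of the fall can be lost.
- A patient held on the lowest-value condition, with a 6-hour pulse of 50 or more and a fall of 14 bpm (15 − 1), is not counted. If a later reading shows a fall of 15 bpm, the listing contains a notable value that the incidence table does not. This case is illustrative.

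**4. QTc incidence.** Removing unscheduled ECGs before 6 hours can only leave the count unchanged or lower it. After 6 hours the text does not settle which value is used:

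- SAP 3.8.4 defines the row as a mean.
- The QTc incidence item in SAP 8.8.4 is not described as being by time point, although neighbouring ECG items are.
- SAP 3.8.6 says that worst-case tables use individual records without averaging.

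Since a mean cannot exceed the maximum of the same values, a count above a threshold based on means is at most the count based on worst values.

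**5. Size.** The number of patients affected is at most the number with a reading after 6 hours. The documents do not give that number. Protocol 5.5.5 requires hourly readings for at least 6 hours but sets no frequency afterwards. The trough time and the spread of readings are not given either. The lower limit of the effect is zero; no upper limit can be derived.

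**6. Consistency.** SAP 8.3.1 says that dose-monitoring vital signs are summarised by the hour in which they were reported, with no upper limit. SAP 3.8.4 stops at hour 6. The two sections need to agree.

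**The case against.** The case against is substantial, and most of it stands as a limit on the point.

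- **The 6-hour window is the protocol's own.** Protocol 9.5.2 plans vital-sign changes for the 6 hours after the first dose and the percent decline in pulse over the same period. The SAP carries this out, so a reader who infers a departure from the protocol would be wrong.
- **Patients kept longer remain visible.** SAP 8.8.3 and 8.8.4 tabulate extended monitoring, hospitalisation, next-day monitoring, and bradycardia events, symptoms and medication, with no 6-hour limit stated. Under SAP 8.8.1, events that the bradycardia forms do not collect are recorded as adverse events. This covers occurrence. It does not give the depth or timing of a measured trough.
- **A fixed window gives both fingolimod arms equal opportunity.** A minimum taken over more readings is lower partly through reading variation, and only patients kept longer have the extra readings. This is why a whole-period summary should supplement the 6-hour tables and not replace them.
- **The readings are in the listings.** They are lost from the summaries, not from the report.

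Three stronger readings are tempting and are not supported. A reader might infer that the trough is in fact cut off, but the protocol says only that it may not have been reached. A reader might take the unscheduled early ECGs to be prompted by symptoms, but no passage says so. And because protocol 1.1 reports an apparent dose response for bradycardia, a reader might infer that the rule narrows the difference between 0.25 mg and 0.5 mg. The documents give no basis for estimating that. The stated purpose in protocol 1.2 is to compare each dose with glatiramer acetate, and no formal test between the doses is planned.

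**Conclusion.** The point holds as a limit of the planned descriptive summary. For patients observed past 6 hours, the tabulated maximum fall in pulse and blood pressure equals or understates the measured one, and the shortfall is informative because one ground for keeping them is that the 6-hour rate was the lowest. The first-dose QTc incidence omits unscheduled ECGs before 6 hours, and its use of values after 6 hours is unclear. The early ECG omission is a separate loss and does not itself hide a late trough.

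The direction follows from the SAP rules alone. Any actual difference requires that later or unscheduled readings were taken and were more extreme than those tabulated. The size cannot be computed from the documents, and a figure built on an assumed trough time, variability and reading schedule would mainly reflect those assumptions. The primary analysis is unaffected. The improvement is worth making because it is cheap.

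**What to change.** 1. Keep the hours 1 to 6 tables as the primary first-dose vital-sign summary.
2. In SAP 3.8.4 and 8.8.4, add a supplementary summary over all monitoring readings (scheduled, unscheduled and extended) giving lowest pulse and blood pressure, maximum change from pre-dose, and Table 4-5 abnormalities. Show by arm the number of patients monitored past 6 hours, with a note that longer monitoring yields more readings.
3. Base the first-dose and second-dose QTc incidence on the worst individual value, including unscheduled ECGs before 6 hours. The mean can stay for the by-time-point row.
4. Align SAP 3.8.4 with 8.3.1 on whether hourly summaries stop at hour 6.

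The cost is SAP wording and a few lines of programming, since the data are already destined for listings. No clinical procedure changes. The drawback is unequal numbers of readings between patients, which the retained 6-hour tables and the note make plain.

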#### 3.8.5 Safety data cutoff and visit windows for summaries on follow-up set

For safety summaries on the safety set, only data which are within 45 days (5 times the half life of FTY720, 9 days) after the last dose of study drug will be considered.

For safety summaries on the follow-up set, all data (including assessments or events more than 45 days after the last dose of study drug) will be considered.

The visit windows below will be used in summaries on the follow-up set.

- 1) Last assessment on study drug
- 2) Day 1 to 45 after study drug discontinuation

- 3) Month 3 (day 46 to 135) after study drug discontinuation
- 4) Month 6 (day 136 to 270) after study drug discontinuation
- 5) Month 12 (day 271 to 540) after study drug discontinuation

For the visit window 1), last assessment on or before the last dose date will be used. For visit windows 2) to 5), assessments collected during the specified day intervals after the last dose date will be used.

